4.17. Data collection on mechanisms of action for azithromycin

Azithromycin MDA has been associated with reduced child mortality, but its mechanism of action in this respect remains unclear. The drug is a broad-spectrum antibiotic with strong activity against many bacterial species and it also has anti-inflammatory properties (Kwiatkowska and Maślińska, 2012). A recent report from the MORDOR trial in Niger documented a lower population prevalence of malaria in communities where under-five-year-old children had received azithromycin than in control villages, but it is not known if this was caused by a direct antimalarial effect or through an indirect pathway (Arzika et al., 2019). Antibiotic treatment might also affect infants' immunity through multiple pathways, including alterations in enteric microbiota and pathogens, enteric and general inflammation, and immune development.

The current trial provides an excellent opportunity for a sub-study to test hypotheses about mechanisms of azithromycin activity against child mortality. In LAKANA, we will test three hypotheses that have been posed but not tested directly earlier, i.e. that azithromycin MDA eliminates malaria parasitaemia and reduces inflammation in the treated host. We will also store biological samples for later laboratory analyses on other hypotheses, to be more specifically determined once the mortality effect is known and some ongoing mechanistic studies elsewhere have been completed.

These are the three hypotheses that we will test in the first phase:

1. Biannual or quarterly azithromycin MDA to 1-11 month (29-364 days) old infants eliminates their asymptomatic malaria, reduces population prevalence of malaria parasitemia, and improves the infants' mean blood hemoglobin concentration.
 - a. Malaria control may be a factor influencing mortality. Azithromycin effect on malaria can in the LAKANA trial be assessed both with direct parasitemia analysis among 4–11-month-old children before and 2 weeks after the fourth azithromycin or placebo treatment and by comparing prevalence of malaria parasitemia among 6–8-month-old and 12–14-month-old children who live in the study villages and who have been eligible to receive 2-4 doses of the study drug. As a marker of health consequences of malaria treatment, we can additionally study blood hemoglobin concentration in the same children.
 - b. To assess community-level prevalence of malaria across communities at the end of the intervention, and a possible carry-over effect, we will also study prevalence of malaria among 1-59-month-old children. This survey will be conducted on visit 9, i.e., when the intervention has lasted for 2 years. The sample size for this survey will be 3000 children aged 1-59 months. The Probability-proportional-to-size (PPS) sampling method will allow that each household in the sample has the same probability of being selected. In each household selected, all 1-59-month-old children will be tested with a malaria rapid diagnostic test.

2. Biannual or quarterly azithromycin MDA to 1-11 month (29-364 days) old infants reduces their general inflammation.
 - a. General inflammation may be an important driver of subsequent disease acquisition and activity. This may be driven by bacteria resident on mucosal surfaces or through the inflammatory modulating properties of azithromycin and can be reflected using simple measure of CRP in small volumes of plasma, in the same groups of children from whom we will do the malaria analyses.
 - b. Larger plasma samples and peripheral blood mononuclear cells from 6–8-month-old and 12–14-month-old children who have been eligible to receive 2-4 doses of study drug will be used for more extensive inflammatory profiling as previously described in our studies on immune activation, inflammation and antibiotic impact in children with HIV (Fitzgerald et al., 2016; Prendergast et al., 2016; Bourke et al., 2019). We will focus on markers we have found to distinguish children with evidence of increased inflammation and immune activation which include, IL6, IL8, IL10, TNF, IL1-RA, soluble adhesion molecules, Serum Amyloid A, markers of disordered thrombogenesis, and markers of cell activation and proliferation (HLA-DR, CD38, Ki67) on naïve and memory CD4 and CD8 populations.
3. Biannual or quarterly azithromycin MDA to 1-11 month (29-364 days) old infants reduces their intestinal inflammation.
 - a. In addition to any impact on general inflammation, intestinal inflammation and environmental enteric dysfunction (EED) could be an important driver of disease. This will be studied by measuring neopterin, myeloperoxidase, and alpha-1-antitrypsin (and possibly other biomarker) concentrations in stools collected from 4–11-month-old infants before and two weeks after the fourth MDA and among 6–8-month-old and 12–14-month-old children who live in the study villages and who have been eligible to receive 2-4 doses of the study drug.

After the trial, we propose to test the following hypotheses (and possibly others) if they are still valid then. For LAKANA, the budget includes only sample collection and storage for these analyses, funding for the actual analyses will be sought later.

4. Biannual or quarterly azithromycin MDA to 1-11 month (29-364 days) old infants leads to improved immunity and vaccine response among 6–14-month-old children.
 - a. Vaccine efficacy is reduced in low-income settings, potentially due to heavy microbial load (Parker et al., 2018). In some settings, it has been possible to improve vaccine response by sanitation and hygiene interventions (Church et al., 2019) or antimicrobials given before vaccination (Uchiyama et al., 2014). This suggests vaccine response enhancement as one of potential mechanisms by which azithromycin could reduce infant mortality. As markers of vaccine response, we will in the LAKANA trial measure antibody titers to rotavirus, tetanus, and measles vaccines. Rotaviral and tetanus antibody concentrations will be analyzed

from plasma samples collected at 6-8 months of age and measles antibody concentration at 12-14 months of age.

b. Azithromycin could also modulate cellular immunity, either directly or indirectly, as we have previously described for the antibiotic cotrimoxazole (Bourke et al., 2019). We and others have shown that the ratio of naïve-to-memory CD4+ and CD8+ T-cells was much lower in African children than in resource-rich settings. Our data shows that this is probably driven by infection driving T cell activation and memory cell expansion despite greater thymic output ([name] et al., manuscript in preparation). In LAKANA, we will determine if azithromycin modulates thymic output, the ratio of naïve to memory CD4 and CD8 sub-populations, their cytokine production and proliferation, and T cell receptor repertoires (TCR) (Gibbons et al., 2014; Sandgaard et al., 2014; Gkazi et al., 2018).

5. Biannual or quarterly azithromycin MDA to 1-11 month (29-364 days) old infants eliminates specific pathogenic microbes from their intestinal tract.

a. Elimination of specific pathogenic microbes is one of the key hypotheses on how azithromycin might reduce child mortality. In LAKANA, this hypothesis can be tested using TaqMan cards of 40-50 potentially pathogenic intestinal microbes and stored stool samples from the trial participants. The analyses can be done from paired stool samples collected from 4–11-month-old infants before and two weeks after the fourth MDA (to track what happens with one MDA dose on an individual level) and from 6–8-month-old and 12–14-month-old children who live in the study villages and who have been eligible to receive 2-4 doses of the study drug (to see a cumulative effect of multiple doses).

6. Biannual or quarterly azithromycin MDA to 1-11 month (29-364 days) old infants modulates their critical bacterially driven metabolic pathways.

a. Metabolic profiling in combination with fecal microbiome will be performed in stored plasma, urine and stool as previously described (Wijeyesekera et al., 2019). Fecal and urine metabolites will be determined by ¹H nuclear magnetic resonance (NMR) spectroscopy. The extent to which the metabolic signature obtained reflects the corresponding microbiota state will be possible combining microbiome data. Special attention will be given to the presence of short-chain fatty acids (acetate/propionate/butyrate/valerate and their isoforms) as well as studying bile-acid metabolism, which play a pivotal role in many aspects of microbial ecology, most importantly in maintaining community homeostasis; their potential contribution to ‘mono-domination’ and ‘stochastic dysbiosis’ following azithromycin administration.

7. Biannual or quarterly azithromycin MDA to 1-11 month (29-364 days) old infants does not cause a sustained reduction in the diversity and immune impact of their intestinal microbiota (measured at one year after the last provided MDA).

a. The composition of the microbiota is known to be influenced by infections and antibiotic usage. Modelling these changes over time is typically challenging due to the large number of potential interactions between

species. However, by using diversity relative to baseline as a measure of displacement from an ‘equilibrium state’, our group has recently developed a simple analytical model of microbiota reconstitution after antibiotic treatment (Shaw et al., 2019). This model successfully shows that short courses of common antibiotics (including ciprofloxacin, clindamycin, minocycline, and amoxicillin) can have year-long effects in adults, causing transitions to alternative microbiota states (quantified using diversity relative to baseline). We will employ this modelling approach to quantify the *in vivo* impact of antibiotics on our patients. By fitting the model to different patient characteristics (e.g., age, weight, MDA) we will also be able to compare model parameters and comment on the potentially different impacts of antibiotics between groups. Simultaneously quantifying microbiota stability and immunity over time, we will be able to study how the two interact and their relative contribution to clinical outcomes using multivariable time series modelling.

Data collection for these analyses will be done in the same sub-sample of 60 clusters as used for the AMR work and other secondary outcomes. From these clusters, we will invite three groups of children for the mechanistic studies:

1. 4–11-month-old infants living in communities that will receive their 4th MDA.
2. 12–14-month-old infants who live in communities that will receive their 6th, 7^h, 8th study MDA and at 9th study visit.
3. 6–8-month-old infants who live in communities that will receive 6th, 7th, 8th study MDA and at 9th study visit.

We will test the first three of the above-described hypotheses (about malaria elimination and reduction of general or intestinal inflammation) from the first group of children, i.e., 4–11-month-old infants living in communities receiving their 4th MDA. From these infants, a study nurse will collect a heel-prick blood sample and a flocculated rectal swab before they have received any MDA. They will collect another heel prick blood sample and a stool sample (or rectal swab if stool collection fails) two weeks after the 4th round of MDA has been conducted in their communities. From the collected blood, the nurse will measure hemoglobin and CRP concentration with an on-site reader and store blood on a filter paper for later malaria diagnostics with DNA-amplification. From the stool sample, a laboratory technician will determine calprotectin and alpha-1-antitrypsin concentrations with commercially available ELISA tests. Additional stool and urine samples will be collected and stored for later analyses (on hypotheses 5-7). In the analysis phase, we will compare prevalence of malaria parasitemia, mean blood hemoglobin and CRP concentration and mean fecal neopterin, myeloperoxidase, and alpha-1-antitrypsin concentration in the three study arms, both before and after the first MDA treatment.

From the second and third group of children (12–14-month-olds who have received 3-4 doses of MDA and 6–8-month-olds who have received 2-3 doses of MDA) we will test hypotheses 2-4, i.e., those about broader general and intestinal inflammation and immune function and development. These infants will be invited to a health facility or a central location in a village - after the MDA visit to their household. At the clinic, a study nurse will receive a home collected stool sample or take a rectal swab if stool collection has failed. S/he will also draw a 5 ml blood sample and collect a 10 ml

urine sample, which will be delivered to a nearby study laboratory by a motorcycle messenger. A laboratory technician will measure Hb, separate plasma and white blood cells, aliquot plasma, urine and stool, and store the samples at -80°C freezer. Approximately once a month, the stored samples will be shipped to a central laboratory at CVD-Mali in Bamako, where another laboratory technician will perform the immunological and inflammatory assays. In the analysis phase, we will compare mean plasma concentrations of vaccine antibodies and selected cytokines, thymic output, the ratio of naïve to memory CD4 and CD8 sub-populations in the three study arms. For the azi-biannual group, we will perform an additional exploratory analysis to assess the impact of timing of the azithromycin dose (given at 1-2 and 6-8 months of age vs at 3-5 and 9-11 months of age).

For hypothesis on microbial clearance and reduction of inflammation, we expect to see the largest effect in infants who have not received azithromycin earlier. We also expect that age of the child may be an effect modifier. Hence, we primarily focus on one time-point (fourth MDA) and a wide age-bracket (4–11-month-old infants). The youngest infants (less than 4 months old) will be excluded for logistical reasons as they will not be invited to sample collection for AMR analyses. Since we want to be able to track individual level changes in test variables, we will collect and analyse samples before and after the MDA. The chosen blood analyses can be completed a battery-operated on-site reader from a small volume taken with a heel-prick – and hence we will not need to take any venous samples from these children.

For the hypotheses on immune function and development, we expect to see the largest effect among infants who have received repeated MDA doses. Therefore, we will choose children at a time when there have been at least 4 rounds of MDA in their home villages. At this point, most or all the 12–14-month-old children have received 3-4 MDA doses and 6–8-month-old children have received 2-3 doses. For the immune function and maturity analyses, we will need a larger blood volume and hence we will take it by a venous puncture, at a study clinic after MDA. Since we are interested in a cumulative effect of multiple MDA doses and only want to do group level comparisons, there is no need for paired sample collection.

The age groups have been selected in a way that there will be no more than one venous blood sample per child during the study. From the 6-8-month of children, we will primarily assess immune development and vaccine responses to tetanus and rotaviral vaccines (given before the age of 6 months). From the 12-14-month of children, we will assess immune development and vaccine response to measles vaccine (given usually between 9 and 12 months of age). From both age-groups, we will also assess malaria prevalence by a DNA amplification test. Immune development and infection are best studied among over-6-month-old children, since by this age infants will have lost most of their passive maternal immunity and will be increasingly susceptible for infection, inflammation, dysbiosis, and EED.

Figure 7 summarises analyses planned to be completed in the first phase.

Study question	Biological specimen	Laboratory analysis	Child age	Level of analysis	Timing of lab sample vs MDA	# of given MDA doses	# of children
Malaria clearance	Blood (dried)	P. falciparum DNA amplification	4-11 mo	Individual	Paired (before and 14 d after)	1	1000
Consequence of malaria clearance	Blood (fresh)	Hemoglobin concentration	4-11 mo	Individual	Paired (before and 14 d after)	1	1000
Reduction of systemic inflammation	Blood (fresh)	CRP concentration	4-11 mo	Individual	Paired (before and 14 d after)	1	1000
Reduction of intestinal inflammation	Stool	Calprotectin concentration	4-11 mo	Individual	Paired (before and 14 d after)	1	1000

Figure 8 summarises biological samples planned to be stored from the study participants (in addition to those, stored in the AMR part of the study). These samples will be used address hypotheses 5-7 of the mechanistic studies as well as for any additional hypotheses formulated during the trial. If all samples were collected and aliquoted as planned, there would be a total of 51,800 stored vials, i.e., these samples will fill one -80°C freezer.

Biological specimen	Child age	MDA or study visit	Timing of lab sample vs MDA	# of given MDA doses	Storage media	Estimated # of aliquots	Volume / aliquot	Storage temperature	# of children
Blood	4-11 mo	4	Before	1-3	Filter paper	2	50 ul	-80°	1000
Stool	4-11 mo	4	Before	1-3	Cryovial	4	1.5 g	-80°	1000
Urine	4-11 mo	4	Before	1-3	Cryovial	3	1.5 ml	-80°	1000
Blood	4-11 mo	4	14 d after	1-3	Filter paper	2	50 ul	-80°	1000
Stool	4-11 mo	4	14 d after	1-3	Cryovial	4	1.5 g	-80°	1000
Urine	4-11 mo	4	14 d after	1-3	Cryovial	3	1.5 ml	-80°	1000
Plasma	6-8 mo	6-9	Before	2-3	Cryovial	4	500 ul	-80°	1350
Peripheral blood mononuclear cells	6-8 mo	6-9	Before	2-3	Cryovial	3	500 ul	-80°	1350
Stool	6-8 mo	6-9	Before	2-3	Cryovial	4	1.5 g	-80°	1350
Urine	6-8 mo	6-9	Before	2-3	Cryovial	3	1.5 ml	-80°	1350
Plasma	12-14 mo	6-9	Before	3-4	Cryovial	4	500 ul	-80°	1350
Peripheral blood mononuclear cells	12-14 mo	6-9	Before	3-4	Cryovial	3	500 ul	-80°	1350
Stool	12-14 mo	6-9	Before	3-4	Cryovial	4	1.5 g	-80°	1350
Urine	12-14 mo	6-9	Before	3-4	Cryovial	3	1.5 ml	-80°	1350

As shown in the figure, we estimate to collect samples from approximately 1,000 infants at the fourth MDA visit and 1,350 thereafter, i.e., approx. 330 - 450 / intervention group.

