 - b. Earlier research has shown that AMR prevalence will increase among treated individuals. How and if this prevalence persists in these treated children 1 year after their treatment has finished but the villages they live in are still on MDA intervention is currently not known. We will assess phenotypic macrolide resistance and resistance against other antibiotics categorized by the World Health Organization (WHO) into "Access" group and/or that may have overlapping mechanisms: meropenem, ceftriaxone, ciprofloxacin, ampicillin, co-trimoxazole, and gentamicin for *E.coli*, and oxacillin, erythromycin, vancomycin, ciprofloxacin, ampicillin, co-trimoxazole for *S. pneumoniae*.
 - c. We will assess genotypic markers of resistance and changes in the intestinal microbiome in children previously treated with azithromycin and we expect that the microbiome in these children has recovered 1 year post treatment and is similar to the microbiome of children in the placebo group.

Outcomes related to the mechanism of azithromycin activity

1. Blood C-reactive protein concentration
2. Blood malaria parasitemia, and hemoglobin concentration
3. Fecal neopterin, myeloperoxidase, and alpha-1-antitrypsin concentrations

Safety outcomes:

1. Incidence of serious adverse events (SAE) within 14 days of study drug administration.
2. Incidence of adverse events (AE) within 14 days of study drug administration.

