10. Quarterly azithromycin MDA to 1-11 month (29-364 days) old infants does not increase carriage of azithromycin resistance bacteria in treated infants 1 year after

their treatment has stopped, who live in a village where MDA intervention has also ceased.

- a. Measured after the intervention for individual child has stopped for 1 year
- b. Separately, there is a similar hypothesis on the effect of biannual azi MDA

11. Quarterly azithromycin MDA to 1-11 month (29-364 days) old infants does not increase carriage of azithromycin resistance bacteria in treated infants 1 year after their treatment has stopped, who live in a village where MDA intervention has continued.

- a. Measured after the intervention for individual child has stopped for 1 year
- b. Separately, there is a similar hypothesis on the effect of biannual azi MDA.

The study hypotheses in terms of azithromycin mechanism of action are the following:

12. Azithromycin MDA reduces malaria prevalence and parasite density, and improves mean blood hemoglobin concentration among 4–11-month-old infants, within 14 days of the MDA
 - a. For these analyses, the two azithromycin can be combined
13. Azithromycin MDA reduces general inflammation (CRP) among 4–11-month-old infants, within 14 days of the MDA
 - a. For these analyses, the two azithromycin can be combined
14. Azithromycin MDA reduces intestinal inflammation (fecal neopterin, myeloperoxidase, and alpha-1-antitrypsin concentrations) among 4–11-month-old infants, within 14 days of the MDA
 - a. For these analyses, the two azithromycin can be combined

There is no predefined hypothesis about the impact of biannual or quarterly azithromycin MDA to 1–11-month-old infants on mortality among 12–59-month-old children living in the same communities, but we will measure group-level differences on this as exploratory analysis.

There are also no predefined hypotheses about the feasibility, acceptability, or equity of the azithromycin MDA intervention.

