6.04. Amount of collected blood and other biospecimens

From most participants, there will be no biological specimen collection.

At four time points, for a sub-sample of approximately 1,350 4-14 month old children and the same number of 49-59 month old children, we will also collect rectal and nasopharyngeal or rectal swabs. At each time point, the children will be different, so for each child, there will only be one sampling. Additionally, at visit 11 we will sample 15-26-months old children who have received 1-4 doses of MDA 1 year earlier in villages that have stopped MDA. In the Koulikoro or Kati (tertiary AMR sample) region we will sample 24-35 months old children who have received 1-4 doses of MDA 1 year earlier and who live in a village that has continued MDA. This will allow us to assess whether azithromycin resistant bacteria survive in individuals that have previously been treated. We will use flocculated swabs for the nasopharyngeal and stool samples. The estimated mass of the collected stool is 200 ug.

From a subgroup of 6-8-month-old or 12-14 month old infants and young children, there will be one venous blood collection, with a total collected blood volume of maximum of 5 ml. The collected volume represents approximately 1% of the infant's total blood volume and it is replaceable from the infants' own blood production within 24 hours. From the same individuals, we will collect 2-10 g of stool and 5-10 ml of urine

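### Section 4.17 contradicts itself on which fecal biomarkers are assayed and on whether the pre-MDA specimen is a rectal swab or stool

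*Combined protocol and SAP*

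**What the plan says.** **Markers.** Section 4.07 lists as a mechanism outcome "Fecal neopterin, myeloperoxidase, and alpha-1-antitrypsin concentrations". Question 4.3 in section 4.02 names the same three markers, and hypothesis 14 in section 5.01 reads "Azithromycin MDA reduces intestinal inflammation (fecal neopterin, myeloperoxidase, and alpha-1-antitrypsin concentrations) among 4–11-month-old infants, within 14 days of the MDA". Within section 4.17, the text under hypothesis 3 commits to "measuring neopterin, myeloperoxidase, and alpha-1-antitrypsin (and possibly other biomarker) concentrations in stools collected from 4–11-month-old infants before and two weeks after the fourth MDA".

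Later in 4.17, the paragraph describing sample collection at the fourth MDA gives the laboratory instruction: "From the stool sample, a laboratory technician will determine calprotectin and alpha-1-antitrypsin concentrations with commercially available ELISA tests". Figure 7, which summarises the first-phase analyses, has one row for intestinal inflammation: calprotectin in stool, individual level, paired before and 14 days after, 1,000 children. The collection paragraph nevertheless ends by planning to compare "mean fecal neopterin, myeloperoxidase, and alpha-1-antitrypsin concentration in the three study arms, both before and after the first MDA treatment".

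**Specimen.** The collection paragraph says that "a study nurse will collect a heel-prick blood sample and a flocculated rectal swab before they have received any MDA". Two weeks after the fourth round it calls for stool, with a swab only if stool cannot be obtained. The hypothesis 3 text instead speaks of "concentrations in stools collected from 4–11-month-old infants before and two weeks after the fourth MDA". The hypothesis 5 text also describes paired stool, Figure 7 gives stool as the paired specimen, and Figure 8 stores four 1.5 g stool aliquots per child both before and after.

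**The concern.** Hypothesis 14 needs three assays. The instruction that a laboratory would act on orders one of them, plus calprotectin, which is not a declared outcome. Neopterin and myeloperoxidase appear neither in that instruction nor in Figure 7, although their means are to be compared between arms.

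Section 4.17 also says that the before-and-after sampling is meant to follow change in individual infants, and Figure 7 labels the analysis as individual and paired. If the first specimen is a swab and the second is stool, a child's difference reflects both what happened in the gut and the switch of specimen. The plan has no rule for recording specimen type, for relating swab results to stool results, or for handling fallback swabs at the second visit.

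**Working it through.** **1. Markers side by side**

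| Place | Calprotectin | Neopterin | Myeloperoxidase | Alpha-1-antitrypsin |
|---|---|---|---|---|
| 4.02, question 4.3 | – | yes | yes | yes |
| 4.07, mechanism outcome 3 | – | yes | yes | yes |
| 4.17, hypothesis 3 text | – | yes | yes | yes |
| 4.17, laboratory sentence | yes | – | – | yes |
| 4.17, Figure 7 | yes | – | – | – |
| 4.17, analysis sentence | – | yes | yes | yes |
| 5.01, hypothesis 14 | – | yes | yes | yes |

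Five places agree on the three declared markers, and the two operational ones do not. The laboratory sentence omits 2 of 3. Figure 7 taken alone omits alpha-1-antitrypsin as well. Section 5.02 does not settle the matter, because beyond malaria parasitemia, CRP and hemoglobin it refers only to other biomarkers.

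**2. Is pre-MDA stool planned? The plan's own vial count**

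Section 4.17 states 51,800 stored vials for Figure 8. Children × aliquots, summed over the cryovial rows:

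- 4–11 months: 1,000 × (4 stool + 3 urine) × 2 time points = 14,000
- 6–8 and 12–14 months: 1,350 × (4 plasma + 3 mononuclear cells + 4 stool + 3 urine) × 2 age groups = 37,800
- Total: 14,000 + 37,800 = 51,800, which reproduces the stated figure (the 4,000 filter-paper spots are not counted in it)

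Pre-MDA stool from 4–11-month-olds accounts for 1,000 × 4 = 4,000 of these. Without it the total would be 51,800 − 4,000 = 47,800. The storage plan therefore requires stool at the pre-MDA visit, where the collection paragraph names a swab.

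**3. Is that stool assigned to hypothesis 14?**

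The collection paragraph reserves the additional stool for hypotheses 5–7 of section 4.17 and gives no time point for it. The text introducing Figure 8 assigns stored samples to hypotheses 5–7 and to any others formulated during the trial. Intestinal inflammation is hypothesis 3 in that list. Its use of the stored stool is neither stated nor excluded.

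**4. What a swab-then-stool pair does**

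Assume, for illustration, that a swab result equals the stool result plus an offset b on the log scale. Let δ be the true mean change in an arm and f the share of infants in that arm with a fallback swab at two weeks.

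- Change in a swab-then-stool child: true change − b.
- Mean change in an arm: δ − b(1 − f). The within-arm change is shifted by specimen type.
- Difference between two arms in the two-week mean: true difference + b(f₁ − f₂). The second term is zero if fallback use is equal. The pre-MDA specimen does not enter.

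The individual change and its arm mean are therefore at risk. The randomized two-week comparison is affected only if fallback use differs between arms. The plan gives no value for b or f, so no size can be put on either effect.

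**The case against.** The strongest reply is that the intent is clear. The outcome list, the study question, the hypothesis and two statements within section 4.17 agree, so the laboratory sentence and Figure 7 can be read as text that was not updated. Pre-MDA stool is planned, and the vial count confirms it. The analysis in section 5.02 compares arms and defines no change score. The sub-study is mechanistic and uses a convenience sample.

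Most of this stands, and it limits the point. A reader might infer that section 4.17 as a whole leaves out neopterin and myeloperoxidase, or that hypothesis 14 and the paired change cannot be derived at all. The documents do not support either reading: the hypothesis 3 text names all three markers in stool at both times, and Figure 8 provides for that stool.

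A reader might also set the swab mass in section 6.04 ("The estimated mass of the collected stool is 200 ug") against Figure 8's stool aliquots and conclude that a swab cannot support the assay. That does not follow. The mass is given in the paragraph on antimicrobial-resistance swabs, Figure 8 describes storage for later work, and the plan does not say how much material an ELISA needs. Nor can a loss of precision be quantified, because the plan gives no within-child correlation.

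What the reply does not answer is that clear intent elsewhere leaves two operational instructions contradicting it. The hypothesis 3 text allows possible further biomarkers, so calprotectin could be an addition, but that does not explain the absence of declared ones.

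**Conclusion.** The contradiction is real and wrong as written, on two counts. First, the laboratory sentence and Figure 7 do not match the declared fecal outcomes; if either is followed, at least two of the three hypothesis 14 markers are not produced. Second, the pre-MDA specimen is a swab in the collection paragraph and stool elsewhere, and no text assigns the stored pre-MDA stool to this outcome; if the paragraph is followed, within-child change is confounded with specimen type for up to 1,000 infants.

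Both counts are conditional on staff working from those passages, and the documents do not show which were used. A specimen difference common to all arms leaves the randomized 14-day comparison unbiased. Unequal fallback use could bias that comparison, but the plan gives no failure rate and no evidence that failure would differ by arm. No stated sample size, alpha or power depends on this point. It should be corrected, but it concerns a secondary objective and does not touch the mortality analysis.

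**What to change.** - In the laboratory sentence of section 4.17 and in Figure 7, replace calprotectin so that both list neopterin, myeloperoxidase and alpha-1-antitrypsin.
- In the collection paragraph, name stool as the hypothesis 14 specimen at both visits, as the hypothesis 3 text and Figure 8 already plan, with a rectal swab as fallback at both.
- Record specimen type for every result, and compute within-child change only from same-specimen pairs.
- Keep the 14-day between-arm comparison in all randomized children with a result as the main analysis, and report swab fallback use by arm. Use a stool-only analysis as a sensitivity analysis only: obtaining stool at two weeks is a post-randomization event that treatment might influence, so restricting to stool, or adjusting for specimen type, could itself introduce bias.
- If pre-MDA specimens have already been taken as swabs, drop the paired fecal change and rest hypothesis 14 on the 14-day between-arm comparison.

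The cost is edits to one paragraph and one figure, a specimen-type field, and two ELISAs (neopterin and myeloperoxidase) in place of one (calprotectin) relative to the laboratory sentence. Pre-MDA stool is already counted in Figure 8. The downside is that some infants will lack a same-specimen pair and drop out of the change analysis.
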